1.3. Background and Significance

Patients who have sustained TBI can have significant decreases in their level of consciousness. This can interfere with the patients' abilities to (1) actively participate in their recovery and can inhibit their ability to breathe without artificial support, (2) obtain adequate nutritional input, and to (3) follow commands to increase range of motion and physical strength. Several of these patients have long intensive care unit and acute care lengths of stay.

The costs associated with the care of patients with TBI are quite high. In 1995, the total direct and indirect financial costs of patients with traumatic brain injuries were estimated at \$56 billion [1]. Schootman et al., estimate 254,500 TBIs required hospitalization in 1996 within the United States, with 5.4 billion US dollars charged to treat these injuries during acute hospitalization [2]. Patient age, increasing severity of injury and urban teaching hospitals were associated with higher charges. McGarry et al estimated the cost of hospitalization for moderate, serious, severe or critical TBI to be \$8,189, \$14,603, \$16,788 dollars, and \$33,537 respectively [3]. Costs also varied by injury type, averaging \$20,084 for gunshot wounds, \$20,522 for motor

vehicle crashes, \$15,860 dollars for falls, and \$19,949 for blows to the head. In this study we seek to demonstrate that the introduction of AAT can increase level of consciousness and cerebral function earlier and, therefore decrease cost of the provision of care to these patients.

Animal Assisted Care (AAC) is an ongoing and well-established program on the Inova Fairfax Medical campus. The main objective of the Animal Assisted Care Program is similar to the Pet Partner's[®] Program objective, which is to improve the patients' well-being through meeting some of their physical and emotional needs with the use of animals in the acute care environment^[4].

The AAC Program provides five modalities of therapeutic interventions (also known as animal assisted interventions (AAI):

1. **Animal Assisted Activities or Visitation**—the Pet Partner Team[®] Training Manual defines these as goal-directed activities designed to improve patients' quality of life through utilization of the human/animal bond. Animals and their handlers must be screened and trained. Activities may be therapeutic but are not guided by a credential therapist. ^[5]
2. **Animal Assisted Therapy (AAT)**--the Pet Partner Team[®] Training Manual defines AAT as utilizing the human/animal bond in goal-directed interventions as an integral part of the treatment process. AAT is directed and/or delivered by a health/human-service professional with specialized expertise and within the scope of practice of his/her profession. AAT is designed to improve human physical, social, emotional and/or cognitive functioning. ^[1] Since a healthcare professional will be measuring patient response, this is the mode of Animal Assisted Intervention which will be utilized for completion of this study. Examples of AAT currently in use at Inova Fairfax Hospital Campus and AAC Program include, but are not limited to: encouraging a patient with decreased LOC to open eyes or to follow commands; having a dog lie beside a terminally-ill patient who is active in the dying process; having the patient throw or kick a ball to the dog to increase strength in extremities; having a dog present to decrease pre-procedure, intra-procedure, and post-procedure stress.
3. **Personal Assistance Therapy**—demonstrates the tasks service animals are able to provide for patients with physical, mental, and/or developmental disabilities. Provides resources and assists patients in completing paperwork to obtain service animal
4. **Service Animal Education**—provides education and support patients who have their service animals accompany them while they are hospitalized. Also, supports and assists staff in understanding their roles and responsibilities when providing care to a patient with a service animal
5. **Visit with Patient's Own Animal**—provides long-term and terminally ill patients with an opportunity to visit with their own dogs and to incorporate their dogs into the patients' plans of care

Over nearly 12 years, the Inova Fairfax AAC program has conducted more than 23,000 interventions to hundreds of patients. At present, the program involves approximately 26 handler/animal teams. The dogs are typically owned by families and live in homes; they are not bred and kenneled specifically and exclusively for the purpose of serving as therapy dogs. Dog owners interested in volunteering with their animal must meet a series of requirements to participate:

- Registration by Pet Partners (formerly known as Delta Society), an international organization specializing in the education, evaluation, and registration of AAI handler/animal teams.
- Completion of Inova Volunteer Services requirements
- Maintenance and provision of documentation of annual health screening requirements for animal and handler
- Adherence to Inova Health System and IFMC AAC policies and procedures

The program adheres to the Association of Professionals in Infection Control (APIC) and Center for Disease Control (CDC) guidelines for safely and responsibly incorporating therapy animals into patient care. Patients who are considered ineligible for the programs include those with allergies or in isolation precautions, with the exception of neutropenic precautions. There have been no incidences of zoonotic transmission of diseases in patients, handlers, or animals from inception to current date.

Few studies have assessed animal assisted interventions and their effectiveness in a quantitative fashion. Even fewer studies have assessed the effectiveness of animal assisted interventions in the critical care setting. In June 1999, Giuliano, Bloniasz, and Bell discussed the implementation of a pet visitation program in critical care, but clearly identify that the program is for visitation or AAA. Furthermore, they state, “We have no quantitative research data to document that these visits are actually helpful to patients in any measureable way, although we certainly hope to have some soon.”^[vii] Coakley and Mahoney assessed patients receiving AAI in an acute care medical-surgical care setting and found that “patients had significant decreases in respiratory rate and pain and a corresponding increase in energy levels following the pet therapy intervention.”^[viii] In this study we hope to provide a quantitative assessment of the effectiveness of AAT in the critical care and acute care environments.

A study done by Cole, Gawlinski, et al in 2007 demonstrated that patients hospitalized with advanced heart failure who received a visit from a volunteer and a dog had lower cardiopulmonary pressures, neurohormone levels, and anxiety levels than did patients visited by a volunteer only and patients given usual care at rest (control group).^{ix}

In 2010, Lee and Higgins^x assessed the use of adjunctive therapies in the critically ill and stated, “No studies were found that examined whether pet visitation has a role in the care of critically patients and the chronically critically ill”. Unfortunately, other than the study done by Cole et al, this is still true three years later.

1.4. Preliminary Studies

Theoretically, there is risk of zoonotic infection to the patient from the dog and from the patient to the dog. However, a study presented by Inova Fairfax Hospital Campus Trauma Services and Animal Assisted Care Program to the Association of Professionals in Infection Control (APIC) in March 2010 demonstrated a zero infection rate in dogs and patients when APIC guidelines are used during AAT.^{xi}

2. STUDY DESIGN AND SUBJECT SELECTION

2.1. Study Type: This is a prospective, experimental study examining the effects of animal assisted therapy on patient’s level of consciousness and cognitive functioning.

2.2. Setting/Location: Research will be conducted at Inova Fairfax Hospital located in Falls Church, VA.

2.3. Duration of Study: The study period will be for 2 years.

2.4. Number of Subjects: In 2011, approximately 100 patients were treated by IFH Trauma Services for TBI with a GCS \leq 8. Target enrollment over the two years will be 100, with approximately 50 patients in each of the two study groups.

2.5. Study Population

2.5.1. Gender of Subjects: Subjects of both genders will be included in the study.

2.5.2. Age of Subjects: The age range of enrolled subjects will be 18-85 years old.

2.5.3. Racial and Ethnic Origin: This pilot study will include English and Spanish speaking patients only; there are no enrollment restrictions based upon race or ethnic origin. However, to ensure understanding of consent, enrollment will be limited to those who speak Spanish or English.

2.5.4. Vulnerable Populations: Participants who do not speak English or Spanish will be excluded. Study participants will have access to translation/interpreter services provided at Inova Fairfax Hospital. If a patient is unable to consent for themselves, a legally authorized representative may consent for them.

2.6. Recruitment: Patients admitted to the Trauma Intensive Care Unit will be considered for the study. The PI will review the trauma patient admission lists for patients and a study team member will ask those meeting inclusion criteria to participate in this research study. In most cases the patient will be unable to consent for themselves and a LAR will be asked to consent. Consent will be obtained by [name] (PI), and the ICU nurses identified as subinvestigators.

The bedside nurse who is caring for the patient on the shift when the patient is enrolled will not be the person who is obtaining consent.

2.7. Inclusion Criteria:

- Patients aged 18-85 years admitted to TICU with severe TBI as identified by GCS ≤ 8 upon admission, or who progress within 96 hours of admission into a severe TBI as evidenced by a decrease in GCS to GCS < 8 .
- Those below GCS 5 will be considered for inclusion when they progress to GCS 5 or above.

2.8. Exclusion Criteria:

Patients...

- who are intoxicated upon admission who experience resolution of neurological symptoms within 24 hours
- with a GCS ≤ 8 , who have no evidence of a TBI and have a blood alcohol level above the legal limit in the state of Virginia (0.8 or higher).
- with a known diagnosis of dementia prior to admission; patients who dislike or are allergic to dogs
- under isolation precautions with the exception of neutropenic precautions for any reason, including MRSA, C Diff, or VRE.
- unable to speak Spanish or English.
- those who would have religious/cultural reasons for avoidance of dogs.
- patients who have a splenectomy

3. STUDY METHODS AND PROCEDURES

All patients admitted to the TICU will have a documented GCS in the medical chart as a part of clinical care. [name] (LH), the study PI, and the Trauma Intensive Care Unit RN subinvestigators will screen the TICU census daily for new patients to identify those admitted with GCS ≤ 8 that meet study criteria. Eligible patients will be followed by the PI or the TICU RNs until the patient is assessed at GCS of 5 or above.

1. Patients with a GCS of 5 or above will be screened for eligibility. Those eligible will be invited to participate and consent will be obtained by study personnel.
2. Consenting subjects will be randomized to the intervention or control arm of the study

3. For patients randomized to the intervention arm, study personnel (PI or TICU RNs) will request a doctor's referral. A referral will be made to LH who will arrange for the patient to receive the intervention with the dog.
4. The control group will be receiving standard of care bedside interventions. During the control measurement period, the only person present will be the bedside nurse who records the measurements.
5. Study personnel will record the RLAS, GCS, Level of Commands, and Movement of Extremities within 24 hours of obtaining consent and order.

Intervention Group

1. When the patient is randomized to the treatment arm, the PI will refer the case to one of the AAC handler/dog teams approved for work on the study for the intervention. The AAC handler will respond within 3 days and will request data measurements be taken by the bedside RN. These measurements will include (see attachments for data collection sheet):
 - A. RLAS Score
 - B. GCS Score
 - C. Level of Command (LOCmd)-0, 1 or 2 or 3-step
 - D. Movement of Extremities
2. Following the recording of the above measurements, the AAC team will provide AAT to the patient.
3. Immediately following the intervention, the same scores will be measured by the same licensed healthcare professional.
4. AAT and measurements of the same data will continue up to three times weekly after the initial measurements and will be listed on data collection sheets. If the patient is unavailable for AAT at the time of the scheduled intervention, the research team will document "unavailable," indicate the reason for unavailability. The patient will remain in the study and data collection will continue until the patient is discharged, reaches RLAS 7, or have been hospitalized ≥ 28 days. If the patient has been discharged from the study but remains in the hospital, he/she may continue to receive AAT.

Control Group

1. When the patient is randomized to the control arm, data measurements will be taken by the bedside RN. Variables to be collected include:
 - A. RLAS Score
 - B. GCS Score
 - C. Level of Command-0, 1 or 2 or 3-step (see same data collection sheet).
 - D. Movement of Extremities
2. The control group will be receiving standard of care bedside interventions. During the control measurement period, the only person present will be the bedside nurse who records the measurements. RLAS, GCS, and Level of Command and movement of extremities will be measured by the same licensed healthcare professional before and after each interaction with the healthcare professional.
3. The PI will be responsible for collecting measurements of the same data up to three times weekly after the initial measurements until they are discharged, reach RLAS 7, or have been hospitalized ≥ 28 days.

When the subject is moved to a different unit, study personnel will continue to be responsible for ensuring the study measurements, as measured by the bedside nurse, are recorded on the data collection form.

Methods for Tracking Recruitment and Retention. Study personnel will:

- Screen the trauma services database to determine the number of patients appropriate for the study.
- Keep detailed notes regarding the number of patients identified as potential participants by the study personnel to determine the percentage of eligible patients approached for inclusion into the study to determine the efficacy of our program to treat this population

- Keep detailed logs reflecting the number of patients approached to participate and the reasons for declining participation and for loss to follow up to determine the willingness of participants to consent to participate and remain in the study.

Preliminary analysis will be completed at the 2 year mark to determine if the appropriate number of subjects have been enrolled, or whether the subject number would need adjustment due to mortality from the disease condition. If more subjects are needed, a request for study extension with increased enrollment approval will be requested.

3.3. Randomization: Randomization will be done on a 1:1 ratio with Microsoft excel generating random participation. Sealed, opaque, sequentially numbered envelopes will be used to select the group in which each patient is enrolled.

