4.2. Method of Data Analysis

Aim 1: To determine if the use of animal assisted therapy in the plan of treatment of patients with TBI results in higher scores on the Ranchos Los Amigos, Glasgow Coma Scale, an increased ability to follow commands, and an increased movement of extremities than those who do not receive AAT.

The difference in RLAS scores from pre-intervention to post the intervention will be the primary outcome for the analysis. The outcome, Δ RLAS, will be defined as RLAS during AAT/sham – RLAS pre-AAT/sham. Δ RLAS from each study visit (AAT or sham) will be averaged over each week of the study (weeks 1-4). To address the primary hypothesis, weekly Δ RLAS will be compared between the AAT group and controls using nonparametric Wilcoxon rank sum tests (Mann-Whitney U tests) in order to determine whether the AAT group has significantly higher Δ RLAS. This analysis will be stratified by weeks 1-4 to determine whether the difference in Δ RLAS between AAT and controls changes over time.

The difference in LOCmd scores and movement of extremities will be a secondary outcome of this study. Δ LOCmds and movement of extremities will be defined similarly to Δ RLAS, as the LOCmds and movement of extremities during AAT/sham – LOCmds and movement of extremities pre-AAT/sham, and the mean Δ LOCmds and movement of extremities will be calculated for each week of the intervention (1-4). Weekly

Δ LOCmd scores and movement of extremities will be compared between study groups (AAT vs. controls) using nonparametric Wilcoxon rank sum tests. This analysis will be stratified by weeks 1-4 to determine whether the difference in Δ LOCmd and movement of extremities between AAT and controls changes over time.

GCS scores are routinely collected every hour by the TICU nursing staff. Medical charts will be reviewed to record the GCS scores during the hour immediately before and immediately after the intervention (or sham) is implemented. Δ GCS will be defined as GCS after AAT/sham – GCS pre-AAT/sham. Weekly Δ GCS scores will be compared between study groups (AAT vs. controls) using nonparametric Wilcoxon rank sum tests. This analysis will be stratified by weeks 1-4 to determine whether the difference in Δ GCS between AAT and controls changes over time.

Aim 2: To determine if the use of animal assisted therapy in the plan of treatment of patients with TBI are discharged with a higher degree of cognitive function than those who did not receive AAT.

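### The doctor's referral is requested after randomisation and in the AAT arm only, which opens the primary comparison to one-arm selection of unknown size and direction

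*Protocol*

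**What the plan says.** Section 3 of the protocol sets out a numbered sequence. Step 1 screens for eligibility and obtains consent. Step 2: "Consenting subjects will be randomized to the intervention or control arm of the study". Step 3: "For patients randomized to the intervention arm, study personnel (PI or TICU RNs) will request a doctor's referral", followed by "A referral will be made to LH who will arrange for the patient to receive the intervention with the dog". Step 5 times the first study scores "within 24 hours of obtaining consent and order".

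The Control Group part of the same section has no referral: "When the patient is randomized to the control arm, data measurements will be taken by the bedside RN".

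In the AAT arm the second score of each pair depends on a session having taken place: "Immediately following the intervention, the same scores will be measured by the same licensed healthcare professional". Section 4.2 defines the primary outcome accordingly, as "RLAS during AAT/sham – RLAS pre-AAT/sham", averaged by week over weeks 1–4 and compared between arms by Wilcoxon rank sum tests.

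Item 1 of the Intervention Group part describes the route differently. There the PI refers the case to a dog team once the patient is randomised, and no doctor's decision is mentioned.

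**The concern.** A decision by a third party, who is not said to be blind to allocation, falls after the envelope is opened and in one arm only. If the doctor does not give the referral, the AAT patient has no session and so no ΔRLAS in any week. If the referral comes late, the patient has no ΔRLAS for the early weeks (counting weeks from enrolment), and the analysis is done week by week. A control patient in the same condition is scored from the start.

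Randomisation protects the comparison only while the patients who supply data in each arm remain comparable. If referral depends on how the patient is doing, the AAT patients with data are a selected part of those allocated, set against unselected controls.

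The loss might also be hard to see afterwards. The logs described in section 3 cover declined participation and loss to follow-up, and the list in section 3.4 of reasons for ending participation does not include a missing referral. Such a patient stays enrolled without primary data.

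**Working it through.** **The plan's own figure.** About 50 patients per arm (sections 2.4 and 4.1). It cannot be reproduced from a power calculation, because no alpha, power, effect size or SD is given. The inputs that are stated, about 100 patients a year for 2 years at 85% consent, give 100 × 2 × 0.85 = 170 before exclusions and deaths. The point below does not depend on this figure; 50 per arm is used only for scale.

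**Step 1: which patients have a primary outcome.**

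| | AAT arm | Control arm |
|---|---|---|
| After randomisation | doctor's referral requested | measurement starts |
| Score pair exists if | an AAT session takes place | a bedside interaction is measured |
| Referral never given | no ΔRLAS in any week | not applicable |
| Referral late | early weeks missing | not applicable |

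**Step 2: illustrative size, no true AAT effect.** The inputs are assumptions, not figures from the protocol: refusal share f = 5%, 10% or 20%; unreferred patients gain one RLAS level in 5% of sessions, others in 20%.

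- AAT mean (referred patients only) = 0.200.
- Control mean = (1 − f) × 0.20 + f × 0.05.
- Difference = f × (0.20 − 0.05).

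| f | AAT patients without ΔRLAS, of 50 | Control mean | Difference | Ratio |
|---|---|---|---|---|
| 5% | 2.5 | 0.95×0.20 + 0.05×0.05 = 0.1925 | 0.0075 | 0.200/0.1925 = 1.04 |
| 10% | 5 | 0.90×0.20 + 0.10×0.05 = 0.185 | 0.015 | 0.200/0.185 = 1.08 |
| 20% | 10 | 0.80×0.20 + 0.20×0.05 = 0.170 | 0.030 | 0.200/0.170 = 1.18 |

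In absolute terms these are differences of 0.0075 to 0.030 of an RLAS level.

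**Step 3: effect on the test.** On a standardised scale, bias = f × D, where D is the deficit in ΔRLAS (in SD) of unreferred patients. One two-sided 5% rank sum test was simulated with 6,000 runs per setting, normal data, 50 randomised per arm, no true effect, and unreferred patients missing from the AAT arm only. The nominal rate of false positives in favour of AAT is 2.5%.

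| f | D = 0 | D = 0.5 SD | D = 1 SD |
|---|---|---|---|
| 5% | bias 0; 2.3% | 0.025 SD; 3.2% | 0.05 SD; 3.9% |
| 10% | bias 0; 2.4% | 0.05 SD; 3.9% | 0.10 SD; 6.7% |
| 20% | bias 0; 2.5% | 0.10 SD; 6.3% | 0.20 SD; 12.4% |

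RLAS is ordinal and will be heavily tied, so these rates show the pattern and are not predictions.

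**Step 4: no deficit (D = 0).** Only numbers are lost. For an assumed effect of 0.57 SD, power falls from 81.3% (50 v 50) to 79.2% (45 v 50) or 76.6% (40 v 50).

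**Step 5: referral decided before randomisation.** Refusals fall outside both arms alike, so the bias from this step is 0 whatever f and D are.

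**The case against.** The strongest reply is that refusal is inferred. Nowhere does the protocol say that a doctor may decline, or how often. The referral may be an administrative order, and item 1 of the Intervention Group part, which omits the doctor, fits that reading. This stands as a limit on size: if every referral is given promptly, nothing is lost. It does not remove step 3, and the two passages need reconciling in any case.

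Second, a reader might infer that contraindications to contact with a dog are checked only once the patient is in the trial. The document does not support that. Section 2.8 already excludes patients for dog allergy, dislike of dogs, isolation precautions, religious or cultural avoidance, and splenectomy, and step 1 of section 3 screens eligibility before randomisation in both arms. Only the doctor's own judgement comes later.

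Third, the protocol does not discard patients who miss a session. Its rule, "If the patient is unavailable for AAT at the time of the scheduled intervention", has the reason recorded and keeps the patient in the study. That is partial mitigation. It addresses a scheduled session, not a referral that was never given, and it supplies no ΔRLAS.

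Fourth, the analysis set may be left to an SAP that is not shown. That is fair for the choice of analysis set. But no SAP can create a within-session change where no session occurred.

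Finally, a late order is not the same as a refusal. It costs early weeks, and the patient still contributes later ones. Only a refusal lasting until discharge, RLAS 7 or day 28 removes the patient altogether.

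**Conclusion.** The point holds in a limited form. The sequence is explicit: the referral follows allocation, applies to the AAT arm only, and stands before the session on which ΔRLAS depends. This leaves the primary comparison open to post-randomisation selection in one arm.

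A reader might go further and conclude that the AAT arm is in fact a doctor-selected subset, or that the protocol excludes unreferred patients from analysis. The document states neither. It gives no refusal rate, and the absence of a ΔRLAS follows from the outcome definition alone.

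Size and direction are therefore unknown. Under the assumed 5–20% refusal and the assumed gain rates, the spurious relative gain is about 4–18%. Over deficits of 0–1 SD the bias is 0 to 0.20 SD. It favours AAT only if unreferred patients would have shown smaller ΔRLAS. It is nil if they respond like the rest, and reversed if they would have shown larger gains. The case for changing the plan is that the repair is cheap and works at the referral step whatever the refusal rate.

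**What to change.** Exchange the order of steps 2 and 3 in section 3:

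- Request the doctor's referral for every consenting patient before the envelope is opened.
- Do not randomise patients for whom it is declined, and log the reason.
- Let the same order serve as the AAT referral for those allocated to AAT.
- Reconcile item 1 of the Intervention Group part with step 3, so that one referral route is described.
- Report sessions missed later by arm with reasons. The reordering cannot prevent these.

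The doctor's decision itself is unchanged; only its timing moves. The cost is about 50 extra requests, for patients who will be allocated to control, plus those for patients declined. A few fewer patients may be randomised. No new staff are needed.

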5.2. Benefits

Patients may not benefit directly from this study; however there will be benefit to our knowledge of animal assisted care and TBI treatment. If this study demonstrates that interaction with animals improves cognitive function in coma patients and decreases length of stay in the intensive care unit and acute care hospital, the impact could be significant from a societal and individual perspective. As such, this study has the potential to elevate animal-assisted therapy into a recognized professional, therapeutic intervention rather than simply a nice diversion for patients during their hospital stay.

5.3. Alternatives: The study is voluntary. The alternative is not to participate in the research.

5.4. Confidentiality: There is risk to the patient for possible exposure of confidential data. To minimize this risk, patients will be assigned a study number; personal identifiers will not be stored in the same database as the study data.

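### Outcomes are not elicited under the same conditions in the two arms, and the control that Section 4.2 calls a sham is standard care

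*Protocol*

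**What the plan says.** **Who is in the room.** Section 3 states for controls, in the general steps and again under Control Group: "During the control measurement period, the only person present will be the bedside nurse who records the measurements". For the AAT arm it says only that a nurse takes baseline scores and then: "Following the recording of the above measurements, the AAC team will provide AAT to the patient". Nothing says who may be present when AAT patients are scored.

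**When the second score is taken.** Under Intervention Group, Section 3 says: "Immediately following the intervention, the same scores will be measured by the same licensed healthcare professional". Section 4.2 says that ΔRLAS, the primary outcome, "will be defined as RLAS during AAT/sham – RLAS pre-AAT/sham". It defines the changes in level of commands and limb movement in the same way, "as the LOCmds and movement of extremities during AAT/sham" less the same items beforehand.

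**What a session may contain.** Section 1.3 lists examples of AAT in use at the hospital. They include "encouraging a patient with decreased LOC to open eyes or to follow commands" and "having the patient throw or kick a ball to the dog to increase strength in extremities".

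**What controls receive.** The abstract and Section 3 describe standard of care, with scores before and after an interaction with a healthcare professional. Section 4.2 calls this period a sham, but the protocol describes no sham procedure.

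**The concern.** A change score compares arms fairly only if it is elicited in the same way in both. Here the written rules differ on two points that bear on an arousal or command score: who is at the bedside, and whether the patient is being actively engaged when scored.

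This is separate from rater expectation. A perfectly objective nurse would still record more movement in a patient who is being asked to move than in the same patient at rest. At stake is what a positive result means. ΔRLAS, ΔLOCmd and Δmovement could favour AAT because of the scoring conditions, with no difference in function once the session is over. The sham label would also lead a reader to think that attention and prompting had been matched between arms.

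**Working it through.** No figure in the protocol bears directly on this point, so the main check sets its sections side by side.

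**1. Timing of the second score**

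| Outcome | Abstract | Section 3 | Section 4.2 |
|---|---|---|---|
| RLAS | post | after the session | opening sentence: post; definition: during |
| LOCmd, movement | during | after the session | during |
| GCS | during | after the session | after (charted hourly score) |

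The timing is not settled. For RLAS, Section 4.2 changes from post to during between one sentence and the next. For controls, Section 3 has the second score after the staff interaction, so Section 3 agrees with itself across arms and Section 4.2 departs from it.

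**2. Conditions at scoring under each reading**

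- *During.* In the AAT arm, the handler and dog are with the patient and the session is under way. If it uses tasks like the examples in Section 1.3, the patient is being encouraged to do what LOCmd (0 to 3-step) and movement of extremities record. In the control arm, only the nurse is present. Conditions differ both in company and in what may be asked.
- *Immediately following.* The session is over, so its tasks are no longer scored directly. But nothing says that the team has moved away or that others are absent, while controls remain under the nurse-only rule. The difference in company remains possible.

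Under neither reading do the written rules secure the same conditions in both arms.

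**3. Is the control a sham?** A sham would need some described imitation of the session, such as a handler visit without the dog, or matched prompting and duration. None is given. The control's interaction has no stated content or length. It is standard care.

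**4. Exposure.** At most 3 sessions a week × 4 weeks = 12 scored sessions per AAT patient. This is a ceiling: sessions are capped, not guaranteed, and patients leave at discharge, at RLAS 7 or at 28 days in hospital.

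**5. Illustration only.** The protocol gives no standard deviation, alpha or effect size. Suppose there is no true difference between arms, but scoring conditions shift one week's mean Δ by *b* SD. Assume two-sided alpha 0.05, the planned 50 per arm (100/2) all contributing, and a normal approximation.

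- Standard error = √(2/50) = 0.20 SD, and u = b/0.20.
- P(significant) = 1 − Φ(1.96 − u) + Φ(−1.96 − u).

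| b (SD, assumed) | u | P(significant) |
|---|---|---|
| 0 | 0 | 5% |
| 0.2 | 1.0 | 17% |
| 0.3 | 1.5 | 32% |
| 0.4 | 2.0 | 52% |
| 0.5 | 2.5 | 71% |
| 0.6 | 3.0 | 85% |

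The protocol does not say which row applies, if any. The table shows only that a moderate shift would matter at this sample size. A larger sample would not remove such a shift.

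**The case against.** The strongest reply is that the trial asks about a package. The rationale compares AAT delivered by handler/dog teams with no AAT, and Section 1.3 defines AAT as a goal-directed intervention. The handler and the encouragement are part of what is randomized. **This stands.** A reader might infer that the comparison is invalid because it cannot separate the dog from the visitor, but the stated aim does not require that separation. Section 1.3 cites a heart-failure study with a volunteer-only group, yet the lack of such a group here is not an error for a package question. What the reply does not cover is measurement: a package comparison still needs its outcomes elicited alike in both arms.

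Other strong inferences also go beyond the text:

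- *That AAT consists of the scored tasks.* The tasks are non-exclusive examples of hospital practice, alongside others such as comfort at the end of life. Overlap is possible, not prescribed.
- *That controls receive no prompts.* The protocol does not say so. Both arms use the same data collection sheet, LOCmd can hardly be scored without giving commands, and a staff interaction lies between control scores. The sheet is an attachment not available here and may fix some of this.
- *That family attend AAT scoring.* They are merely not excluded. Only the handler/dog team is certain to attend the session.
- *That a gain during a session is close to automatic.* A prompt need not produce a response in patients who may enter at GCS 5.
- *That Section 5.2 credits any gain to animals.* The sentence is conditional, "If this study demonstrates that interaction with animals improves cognitive function in coma patients", and sits under Benefits. It is not a rule for drawing conclusions.

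**Conclusion.** The point holds in limited form. The nurse-only rule is written for controls alone. The during definition in Section 4.2 conflicts with Section 3 and, if followed, has AAT patients scored in the middle of the intervention. The sham label has no procedure behind it. Together these mean that the plan as written does not ensure equal conditions of elicitation for the primary outcome and two secondary outcomes. ΔGCS is less exposed, because Section 4.2 takes it after the session from charted scores.

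The direction of concern is towards AAT; the size is unknown. It depends on what sessions contain, who attends, what nurses ask of controls and which timing is used, and the protocol fixes none of these. The percentages in the illustration rest on assumed shifts and are not estimates for this trial. The point should be corrected, but it does not make the AAT-versus-usual-care comparison invalid.

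**What to change.** 1. **One scoring time.** Reconcile the abstract, Section 3 and Section 4.2 so that the post score is taken after the session in both arms.
2. **One scoring condition.** In Section 3, apply one presence rule to pre and post scoring in both arms: bedside nurse only, handler/dog team stepped away and silent, no visitors. The nurse gives the same short fixed set of commands, none involving the dog, and scores from the responses.
3. **Wording.** In Section 4.2 replace sham with standard-care period. State conclusions as the effect of handler/dog AAT sessions added to usual care, not of the animal alone.

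This needs a few sentences and one short command list, used by the nurse who already scores. No extra arm, patients or staff are required. The downsides are small: the team and any visitors step back briefly at each scoring, and a response shown only while the dog is present is no longer counted. The changes make scoring comparable. They do not separate the dog from the handler, and the package question does not need them to.
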